the anaesthesiologists in charge of the surgery. The anaesthesiologists, accessors, and patients will be blinded to the type of drug administered during surgery. The administered drug will be unmasked, with the agreement of the primary investigator, when esketamine-related severe adverse events occur (such as an allergy to the study drug) after the intervention and before the termination of surgery.

Outcomes

The primary outcome is the proportion of participants attaining remission (defined as a MADRS score less than or equal to 10) three days after surgery, based on an evaluation by blinded accessors at the bedside.

Secondary outcomes, including the differences in MADRS scores at three days and five days (or discharge) after surgery and the rates of patients achieving a response (MADRS scores reduced to or lower than half of the baseline MADRS score), the rate of severe pain within 72-hour postoperative period (severe pain is defined by the numeric rating scale pain scores equal to or more than 7).²¹

Safety outcomes include manic symptoms evaluated by the 11-item Young Mania Rating Scale (defined by YMRS scores more than or equal to 5) within the 3-day postoperative period,²² psychotic symptoms measured by a nonzero score on four particular items of the Brief Psychiatric Rating Scale (unusual thought content, suspiciousness, hallucinations, and conceptual disorganization) during the three days after surgery,^{23, 24} dissociative symptoms accessed by a nonzero score on the Clinician-Administered Dissociative States Scale within three days after the operation,²⁵ and all drug-related adverse events during surgery or before discharge.

Data management

The clinical data will be recorded and managed with the electronic database. The paper version materials including the protocol, the case reported forms, informed consent forms, and electronic version database will be preserved by the primary investigator and stored in the independently locked strongbox in Beijing Tiantan Hospital.

Sample size calculation

It has been reported that the remission rate difference in the antidepressant effects between esketamine and ketamine was 3.8% in treatment-resistant depression

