also be reported. Because of the potential for type I errors due to the lack of adjustment for multiple comparisons, the findings for secondary outcomes or sensitivity analyzed should be interpreted as exploratory. All analyses will be performed by using Stata version 14.0.

Safety consideration

Once adverse events occurred during drug intervention, the principal investigator will be informed immediately. Based on the severity of the adverse events and the relation to esketamine, the unmasking process will be considered by the principal investigator. All the adverse events that occurred during the trial will be recorded in detail and closely monitored until stabilization or the time of the study intervention is not the cause for adverse events. All the adverse events will be reported to the Institutional Review Board by the principal investigator.

Patient and public involvement

Patients and the public were not involved in the trial design. Participants will have access to the findings of the study on request.

Ethics and dissemination

This study was approved by the Institutional Review Board of Beijing Tiantan Hospital, Capital Medical University, Beijing, China on October 30, 2020 (KY-2020-058-02). It has been registered on clinicaltrials.gov on June 11, 2020 (NCT04425473). The first participant was recruited on February 19, 2021. The conclusions of this study will be published in peer-reviewed journals.

Discussion

This study is a randomized placebo-controlled double-blinded clinical trial that aims to explore the effect of esketamine on depressive symptoms in the major surgery population. The participants will be administered 0.2 mg/kg esketamine intravenously within 40 min with the suturing of the incision. The efficacy and safety endpoints will be observed during the perioperative period and in the long term after major surgery.

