To compare all the safety events of surgery and study drugs administered intraoperatively in terms of psychiatric symptoms, dissociative symptoms and manic

symptoms, and adverse and serious adverse events during the study period. Further exploratory objectives were to evaluate the postoperative 1-, 3-, and 6-month quality of life (WHODAS 2.0) and depressive symptoms.

Study endpoints

Primary efficacy

The remission rate of depressive symptoms at 3 days postoperatively was defined as a Montgomery-Åsberg Depression Rating Scale (MADRS) score less than or equal to 10. [2]

Secondary efficacy

The remission rate of depressive symptoms at discharge was defined as MADRS scores less than or equal to 10.

The response rates of depressive symptoms 3 days after surgery and at discharge.

The rate of moderate-to-severe pain during the first postoperative 3 days and severe pain were defined as numeric analogue scale (NAS) scores greater than 3.

Changes in further efficacy: Changes in depressive symptom scores at 1 month, 3 months, and 6 months postoperative; and the WHODAS 2.0.

Safety efficacy

Psychiatric complications: drug-related manic, psychotic, and dissociative symptoms during the first 3-day postoperative period. [3,4]

Surgery-related complications

3. Study overview

This study is a multicenter, randomized, placebo-controlled and double-blinded clinical trial. The primary null hypothesis of this study is that there is no difference in the 3-day postoperative remission rate between 0.2 mg/kg esketamine administered intraoperatively for 40 min and placebo administered at the same time in the same volume.

Patients undergoing major surgery, combined with moderate-to-severe depressive symptoms defined as those with a Patient Health Questionnaire 9 (PHQ-9) [5] score

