Patient-reported duration of illness		
< 1 month	n (%)	n (%)
1-3 months	n (%)	n (%)
Coexisting medical condition		
Diabetes	n (%)	n (%)
Hypertension	n (%)	n (%)
Stroke	n (%)	n (%)
Heart disease	n (%)	n (%)
Chronic pain	n (%)	n (%)
MDD	n (%)	n (%)
Motor dysfunction	n (%)	n (%)
Surgical history	n (%)	n (%)
ASA physical status	n (%)	n (%)
Charlson's comorbidity scores	Mean (SD)/median (IQR)	Mean (SD)/median (IQR)
Severe depressive symptoms	n (%)	n (%)
Recurrent malignancy	n (%)	n (%)
Preoperative assessment		
PHQ-9	Mean (SD)/median (IQR)	Mean (SD)/median (IQR)

MADRS	Mean (SD)/median (IQR)	Mean (SD)/median (IQR)
GAD-7	Mean (SD)/median (IQR)	Mean (SD)/median (IQR)
HADS	Mean (SD)/median (IQR)	Mean (SD)/median (IQR)
WHODAS 2.0 scores	Mean (SD)/median (IQR)	Mean (SD)/median (IQR)
Z-WHODAS 2.0	Mean (SD)/median (IQR)	Mean (SD)/median (IQR)
Type of surgery	n (%)	n (%)
Other ^a	n (%)	n (%)

Data are shown as the mean (SD)/median (interquartile range) and numbers (%).

Table 2. Primary outcome and Secondary outcomes.

Characteristics	Esketamine group	OR/Difference		P value
		Control group	(95%CI)	
Primary Outcome				
Remission on day 3	n (%)	n (%)	OR (95% CIs)	x
Secondary Outcomes				
NRS Pain scores >3, 0-48 Hours	n (%)	n (%)	OR (95% CIs)	x
Rescue analgesia, 0-48 Hours	n (%)	n (%)	OR (95% CIs)	x
Assessments on POD3				
MADRS	median (IQR)	median (IQR)	D (95% CIs)	x
GAD-7	median (IQR)	median (IQR)	D (95% CIs)	x
HADS	median (IQR)	median (IQR)	D (95% CIs)	x
PHQ-9≥10	n (%)	n (%)	OR (95% CIs)	x
Response	n (%)	n (%)	OR (95% CIs)	x
Assessments on discharge				
MADRS	median (IQR)	median (IQR)	D (95% CIs)	x
GAD-7	median (IQR)	median (IQR)	D (95% CIs)	x
HADS	median (IQR)	median (IQR)	D (95% CIs)	x
PHQ-9≥10	n (%)	n (%)	OR (95% CIs)	x
Response	n (%)	n (%)	OR (95% CIs)	x
Remission	n (%)	n (%)	OR (95% CIs)	x
Length of hospital stay	median (IQR)	median (IQR)	D (95% CIs)	x
Adverse events				
PONV, 0-48 Hours	n (%)	n (%)	OR (95% CIs)	x
Dissociative symptoms (CADSS≥5)	n (%)	n (%)	OR (95% CIs)	x
Psychotic side effects (BPRS 4 items≥5)	n (%)	n (%)	OR (95% CIs)	x
Manic symptoms (YMRS≥5)	n (%)	n (%)	OR (95% CIs)	x
Delirium	n (%)	n (%)	OR (95% CIs)	x
Infection after surgery	n (%)	n (%)	OR (95% CIs)	x
Bleeding events	n (%)	n (%)	OR (95% CIs)	x
Thrombus events	n (%)	n (%)	OR (95% CIs)	x

Figure 1 Flow chart and consort diagram of the study

Figure 2 Primary outcomes and MADRS scores

Figure 3 Subgroup analysis and interactions

10. Reference

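### The Protocol and SAP disagree on whether safety events must be drug-related to count, and over what window

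*SAP*

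**What the plan says.** Some text restricts the events that count:

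- SAP section 2, Study endpoints: "Psychiatric complications: drug-related manic, psychotic, and dissociative symptoms during the first 3-day postoperative period".
- Protocol, Outcomes, last safety item: "all drug-related adverse events during surgery or before discharge".
- SAP section 3 describes perioperative follow-up for complications, again qualified as related to the drug.

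Other text does not:

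- SAP section 2, Study objective: "To compare all the safety events of surgery and study drugs administered intraoperatively", followed by "adverse and serious adverse events during the study period".
- Protocol, Safety consideration: "All the adverse events that occurred during the trial will be recorded in detail".
- Protocol, Outcomes: mania, psychosis and dissociation are defined by scale scores within three days, with no causality condition.
- SAP section 9, Table 2: eight adverse-event rows, among them "Manic symptoms (YMRS≥5"), none of them conditional on cause. There is no row for all adverse events or for serious adverse events.
- SAP section 2 also lists "Surgery-related complications" as a separate safety endpoint.

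The only stated use of an event's relation to esketamine is the unmasking decision (Protocol, Safety consideration).

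**The concern.** In a randomised placebo comparison, the difference between arms does the attributing. Events the drug does not cause should occur about equally often in both arms, and an excess on esketamine estimates the harm. A case-level opinion on cause, applied before counting, replaces part of that comparison with judgement. After major surgery the judgement is difficult, because psychiatric and general events have many competing causes.

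The conflict matters most for general adverse and serious adverse events. There the Protocol outcome is explicitly limited to related events up to discharge, and no row in Table 2 overrides it. Two analysts could follow these documents faithfully and produce different safety tables, with the choice open until the data are seen.

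**Working it through.** The plan states no safety event rate and claims no power for safety, so there is no figure of its own to reproduce. The main check is a comparison of the texts.

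**Step 1: who counts, and when**

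| Event type | Restricting text | Unrestricted text |
|---|---|---|
| Manic, psychotic, dissociative symptoms | SAP section 2 endpoint: drug-related, 3 days | Protocol Outcomes: scale score, 3 days; SAP Table 2: scale score |
| General adverse and serious adverse events | Protocol Outcomes: drug-related, surgery to discharge | SAP section 2 objective: all, over the study period; Protocol Safety consideration: all recorded |

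For the psychiatric symptoms the window agrees wherever one is stated (three days), and only the relatedness condition conflicts. For general events both conflict.

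**Step 2: is there a rule that resolves it?** No assessor, timing or criteria for relatedness are given for the endpoint. The Safety analysis paragraph in SAP section 9 plans counts, percentages and odds ratios by arm but does not list the variables.

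**Step 3: what a filter would do.** Let the true event rates be p_E and p_C, and let a blinded assessor keep the same fraction k of events in each arm. Then:

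- observed difference = k × (p_E − p_C), which shrinks with k;
- observed ratio = (k × p_E)/(k × p_C) = p_E/p_C, which is unchanged.

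**Step 4: size, as an illustration only.** Planned total 564, so n = 564/2 = 282 per arm. The rates and k are assumptions. With observed rates a and b, m = (a + b)/2 and two-sided alpha 0.05:

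power = Φ{ [(a − b) − 1.96 × se0] / se1 }, se0 = √[2m(1 − m)/n], se1 = √{[a(1 − a) + b(1 − b)]/n}.

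Example, true 10% versus 5% and k = 0.5: a = 0.05, b = 0.025, m = 0.0375, se0 = 0.0160, se1 = 0.0160. Power = Φ[(0.025 − 0.0314)/0.0160] ≈ Φ(−0.40) ≈ 0.35.

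| Fraction kept | 10% v 5%: difference, power | 15% v 8%: difference, power |
|---|---|---|
| 100% | 5.0 points, 62% | 7.0 points, 74% |
| 75% | 3.75 points, 49% | 5.25 points, 60% |
| 50% | 2.5 points, 35% | 3.5 points, 43% |
| 25% | 1.25 points, 19% | 1.75 points, 24% |

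The risk ratio stays at 2.0 in the first scenario and 1.875 in the second.

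**The case against.** The best defence is that this is loose wording and the planned analysis is not filtered. Much of that stands. The Protocol's three psychiatric outcomes and all eight Table 2 rows are free of any causality condition. The SAP's psychiatric sentence cites the papers for the dissociation and mania scales, which points to score-based endpoints. Placed next to "Surgery-related complications", the term drug-related can be a label for symptoms typical of this drug class. No adjudication step is described anywhere. A reader might infer that all the safety endpoints count only related events, or that psychiatric events will certainly be filtered. The documents support neither.

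The defence does not reach general adverse events. There the Protocol's limit is explicit, and Table 2 has no all-event or serious-event row that would supersede it.

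On the window, the SAP's 1-, 3- and 6-month assessments are described for quality of life and depressive symptoms, and SAP section 3 ties follow-up for complications to the perioperative period. So it is not established that the SAP counts a serious event after discharge and the Protocol does not. The conflict turns on an undefined term.

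A reader might also infer that relatedness judgements would create a false excess in one arm. That needs different labelling by arm. Anaesthesiologists, assessors and patients are blinded, and nothing in the documents shows that assessors could tell the allocation.

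Finally, an accurate causality judgement would remove background events and sharpen the comparison. But without stated criteria, and with drug-caused and background events looking alike to a blinded assessor, the plan gives no ground for expecting that accuracy.

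**Conclusion.** The inconsistency is real and lies in the text of both documents. It concerns relatedness for the psychiatric endpoint, and relatedness and window for general adverse and serious adverse events. Filtering follows from the Protocol's wording for general events. For psychiatric events it is one possible reading, and the Protocol definitions and Table 2 point the other way.

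If a filter were applied, blinded and equal in both arms, the absolute difference would fall in proportion to the events dropped and detection would weaken, while the ratio would be unaffected. The direction rests only on equal retention in both arms. The power figures rest entirely on assumed rates and retention fractions and are not estimates for this trial.

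The restriction does not itself lose data, because the Protocol has all adverse events recorded. The point should be corrected, but it does not touch the primary efficacy analysis.

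**What to change.** 1. Delete the drug-related condition from the SAP section 2 psychiatric endpoint and from the Protocol's adverse-event outcome, and align the follow-up sentence in SAP section 3.
2. State in SAP section 9 that all scale-defined psychiatric events and all recorded adverse and serious adverse events are compared by arm whatever their attributed cause. Add rows for any adverse event and any serious adverse event to Table 2, with relatedness as a supplementary column only.
3. Define the study period for safety identically in both documents, for the events already being recorded. Collecting adverse events at the 1-month contact is not required.

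The psychosis and dissociation cut-offs also differ (nonzero in the Protocol, 5 or more in Table 2). That is a separate point, but it must be settled before events are called scale-defined.

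The cost is wording and two table rows. Recruitment began in February 2021 and the SAP of March 2024 is marked final, so the change should be a dated amendment, made before allocation is unblinded if that is still possible. The small downside is higher stated event counts, including background surgical events.

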patients.²⁶ In the perioperative population with depressive symptoms, the remission rate was reported to be 23.1% in the ketamine group and 9.3% in the placebo group based on the PASSION study at our research site. We assumed that the remission rate in the esketamine group will be 19.3% and that in the placebo group will be 10%. A sample size of 506 participants will provide 80% power to show the difference between the esketamine group and the placebo group (with a ratio of 1:1), including 1 interim analysis by using a 2-sided significance level of 0.05.²⁷ With the consideration of a 10% attrition rate, the total sample size is planned to be 564.

Interim analysis

The planned interim analysis will be performed after 424 patients (75% of the total sample size) completed the follow-up. This interim analysis will be based on the ITT principle, and the P value will be set at 0.019 following adjustment by O'Brien-Fleming methods.²⁸

Statistical analysis

Continuous variables will be reported as the mean (standard deviation) for normally distributed data and the median (interquartile ranges) for skewed distributions. Categorical variables will be reported as the number (proportion), and the relative risk with its 95% confidence intervals will be calculated. The difference between groups will be reported with 95% confidence intervals of absolute differences calculated by independent t-tests for continuous variables and using the Hodges–Lehmann method for skewed variables. The primary endpoint of remission rate at 3 days after surgery will be analyzed by using the chi-square test or Fisher's exact test. The secondary outcomes will be analyzed using t-tests, Mann–Whitney U tests, and chi-square or Fisher's exact tests as appropriate. The adjusted odds ratios will be estimated by using a logistic regression model by taking into account the unbalanced baseline variables, age, sex, the severity of depressive symptoms, and pain severity after surgery.

For missing values, both imputations with the mean or median or the last observed assessment and multiple imputations will be applied. Sensitivity analysis for different imputation plans will be used to explore the statistical nature of the missing data. All statistical tests will be 2-sided at a significance level of 0.05 and the effect sizes will

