The null hypothesis of no difference in remission rate between the two arms of intervention will be analysed by a two-sided test at the 5% level of significance.

$$H_0: \lambda_1/\lambda_2 = 1$$

$$H_1: \lambda_1/\lambda_2 \neq 1$$

where λ_1 is the remission rate at postoperative day 3 in the group treated with esketamine and where λ_2 is the same timepoint in the group treated with placebo.

5. Sample size determination

The difference in the remission rates of antidepressant effects between esketamine and ketamine was reported to be 3.8% in patients with treatment-resistant depression. In the perioperative population with depressive symptoms, the remission rate was reported to be 23.1% in the ketamine group and 9.3% in the placebo group on the basis of the PASSION study at our research site. We assumed that the remission rate in the esketamine group would be 19.3% and that in the placebo group would be 10%.

A sample size of 506 participants provided 80% power to show the difference between the esketamine group and the placebo group (with a ratio of 1:1), including 1 interim analysis with a two-sided significance level of 0.05. Considering a 10% attrition rate, the total sample size is planned to be 564.

6. Interim analysis

The planned interim analysis will be performed after 424 patients (75% of the total sample size) have completed the follow-up. This interim analysis is based on the

intention-to-treat principle, and the p value is set at 0.019 following adjustment by the O'Brien-Fleming method. ^[6] The trial will be stopped after interim analysis if a significant difference between the groups is detected.

7. Population analysis

Total population

This population will comprise all the subjects screened and for whom a record exists in the study database. This population will be used for listing adverse events occurring prior to randomization and reasons for withdrawal occurring prior to randomization.

Modified Intent-to-Treat Population

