The intent-to-treat (ITT) population will include all the subjects after randomization and who received esketamine or placebo during surgery. After randomization, it is assumed that all participants have been administered a placebo or esketamine. The modified intent-to-treat population will be excluded from the analysis after randomization situations no longer meet the eligibility criteria, patients who do not have surgery, or patients who cannot undergo follow-up due to surgery-related complications, such as aphasia or coma. The modified ITT population will be tested for demographic characteristics and efficacy and safety outcomes. The population will be used for primary analysis of the efficacy and safety outcomes.

Per-Protocol population

The per protocol (PP) population will comprise all participants except subjects who are confirmed as protocol transgressors. The subjects excluded from the PP population will be confirmed before being blind. This population was used for sensitivity analysis to determine the effect of missing data. In the PP population, subjects will be analysed according to the treatment received and the real events after postoperative assessments.

8. Statistical considerations

The data will be analyzed by Stata 16.0 software (Stata Corp LP, College Station, TX,

USA) and all significance tests will be two-sided, with an alpha setting of 0.05 and 95% confidence intervals confirmed.

Subgroup analysis

The rate of postoperative 3-day remission will be presented at each level of the variables listed below. The degree of change in the treatment effect of each subgroup at different levels will be evaluated via an interaction test.

Multiplicity

The single primary outcome was defined in the protocol, and all other efficacy variables were treated as secondary or other. The only comparison of interest in this study was between esketamine and placebo, and there was no need to adjust for multiple comparisons. All estimates of treatment effects for secondary endpoints will be presented with 95% confidence intervals, no inferential tests will be performed, and only exploratory tests with simple descriptions of these endpoints will be performed.

Missing Data

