The remission rate of depressive symptoms at 3 days postoperative will be summarized by treatment group via the chi-square test or Fisher's exact test to compare the differences between groups in the m-ITT population. The risk ratio for the intervention comparison is presented, and the 95% CI is reported. The results are

also displayed graphically on a histogram plot.

Secondary efficacy analysis

All secondary endpoints are based on the m-ITT population. For categorical variables, which are presented as frequency counts and percentages, a two-sided Pearson's χ^2 test or Fisher's exact test will be used, as appropriate. The odds ratios and 95% CIs were calculated. For continuous variables, prior to performing the statistical analysis, the assumptions of normality and homogeneity of variance of the residuals of quantitative variables were tested via the Shapiro-Wilk test and Levene's test, respectively. For efficacy analysis, a t test (normal variables) or the Mann-Whitney U test (skewed variables) will be used, as appropriate. The absolute difference and 95% CIs were calculated via the Mann-Whitney U test and the Hodges-Lehmann method.

Safety analysis

Safety endpoints will be assessed in the total population. The related variables are presented as frequency counts and percentages in both the esketamine group and the control group, odds ratios and 95% CIs.

Interaction with subgroups

A summary forest plot will be presented on the basis of the predefined subgroups, and interactions between them will be investigated for the primary endpoint. Exploratory subgroup-specific summary statistics and p values for interactions are presented. A separated logistic model was applied for interaction to identify its effect significance. The subgroup analysis included the following covariates: unbalanced baseline variables, age, sex, severity of depressive symptoms and pain severity after surgery.

Main results with Tables

Table 1. Demographic and preoperative characteristics of the total population.

Characteristics	Esketamine group	Control group
Sex		
Female	n (%)	n (%)
Male	n (%)	n (%)
Age, yr,	Mean (SD)/median (IQR)	Mean (SD)/median (IQR)
Height, cm,	Mean (SD)/median (IQR)	Mean (SD)/median (IQR)
Weight, kg,	Mean (SD)/median (IQR)	Mean (SD)/median (IQR)
Education	n (%)	n (%)
Married	n (%)	n (%)
Living state (alone)	n (%)	n (%)
Employed	n (%)	n (%)
Currently smoke	n (%)	n (%)
Alcohol intake		
Never	n (%)	n (%)
Occasional	n (%)	n (%)

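### The interim stopping test is placed on the ITT principle and the primary test on m-ITT, and the SAP does not say which result governs after an early stop

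*SAP*

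**What the plan says.** **Interim.** The protocol's interim section reads: "This interim analysis will be based on the ITT principle, and the P value will be set at 0.019". SAP section 6 repeats this ("intention-to-treat principle, and the p value is set at 0.019") and times the look "after 424 patients (75% of the total sample size) have completed the follow-up". It adds a stopping rule that leaves no discretion: "The trial will be stopped after interim analysis if a significant difference between the groups is detected".

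**Primary analysis.** SAP section 7, under the heading for the modified ITT population, says: "The population will be used for primary analysis of the efficacy and safety outcomes". The Main Model in SAP section 9 uses the chi-square or Fisher test "to compare the differences between groups in the m-ITT population".

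**The two sets.** SAP section 7 describes ITT first: "The intent-to-treat (ITT) population will include all the subjects after randomization and who received esketamine or placebo during surgery". It then describes m-ITT as leaving out three groups of randomised patients: those later found ineligible, those whose operation did not take place, and those who cannot be followed up because of a surgical complication. The protocol has no m-ITT set and names no set for the final test.

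**What is absent.** Neither document says that m-ITT also applies at the interim, or which analysis is the trial's primary result if it stops there.

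**The concern.** A group-sequential boundary is derived for one test statistic followed over accumulating data. Here the statistic that can end the trial and the statistic reported as primary are, as written, computed on different sets. If the trial stops, its published primary p-value would come from m-ITT, and that test was never required to meet 0.019. The reverse can also occur: the trial continues because ITT misses the boundary although m-ITT would have met it.

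At stake is the coherence of an early stop. A trial that ends at 424 patients because of a significant difference should not then have to report a primary result that misses the threshold used to end it. The choice of governing result should also not be left until both are known.

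**Working it through.** **1. The plan's own figure.** With O'Brien-Fleming-type spending, two-sided 0.05 and information fraction t = 0.75, the nominal p at the first look is 4 × [1 − Φ(z₀.₉₈₇₅/√t)] = 4 × [1 − Φ(2.2414/0.8660)] = 4 × [1 − Φ(2.588)] = 0.0193. This matches the stated 0.019. The classic O'Brien-Fleming boundary gives 0.0200. The timing also fits: 0.75 × 564 = 423, against 424 stated. The boundary itself is not in question.

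**2. How little it takes.** Take 424 patients as 212 per arm. The uncorrected chi-square test is z = (p₁ − p₂)/√[p(1 − p)(1/n₁ + 1/n₂)], with p the pooled rate. The placebo count of 21/212 (9.9%) is close to the planned 10%. The esketamine count of 38 is the smallest that crosses 0.019 against it, since 37 gives p = 0.0237. The example is therefore placed at the boundary on purpose.

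| Analysis | Esketamine | Placebo | z | p | Below 0.019? |
|---|---|---|---|---|---|
| ITT | 38/212 | 21/212 | 2.385 | 0.0171 | yes, stop |
| m-ITT, one esketamine remitter excluded | 37/211 | 21/212 | 2.281 | 0.0225 | no |
| m-ITT, four placebo non-remitters excluded | 38/212 | 21/208 | 2.308 | 0.0210 | no |

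First row in full: difference 0.1792 − 0.0991 = 0.0802 (from unrounded rates); pooled rate 59/424 = 0.1392; standard error √(0.1392 × 0.8608 × 2/212) = 0.0336; z = 2.385.

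**3. How often.** The documents give no m-ITT exclusion rate, so 1%, 2%, 5% and 10%, equal in both arms, are assumptions. For each, 400,000 interim looks were simulated at 212 per arm with the planned rates of 19.3% and 10%, and both p-values were computed in the same patients. The lower end of each range counts excluded patients as non-remitters in ITT. The upper end keeps their own outcomes. The probability of stopping on ITT was 0.59 to 0.65.

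| Excluded per arm | Stops with m-ITT p ≥ 0.019 | Trials that stop with m-ITT p ≥ 0.05 |
|---|---|---|
| 1% | 1.0–2.6% | about 0 |
| 2% | 1.3–4.1% | under 0.1% |
| 5% | 2.1–7.6% | at most 0.3% |
| 10% | 2.9–12.5% | at most 1.4% |

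The reverse case (m-ITT below 0.019, no stop on ITT) occurred in 0.6–1.0% of trials at 1% exclusions and 1.5–2.1% at 5%.

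**4. With no true effect (10% in both arms).** About 1.9% of trials stop falsely. Of those stops, m-ITT does not confirm 4–10% at 1% exclusions and 9–24% at 5%. In absolute terms the 5% case is 0.0017 to 0.0046 of all trials.

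**5. Overall type I error.** A two-look simulation used ITT at 0.019 for the interim and m-ITT at about 0.044 for the final test. The documents state no adjusted final level; 0.044 is assumed because, with 0.019 at the interim, it brings the total to 0.05. With equal exclusions the overall error was 0.049–0.052, against 0.049–0.051 when one set is used at both looks.

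**The case against.** **The two sets may be meant as one.** The interim text speaks of the ITT principle, not the ITT population. The only ITT definition stands under the m-ITT heading and already requires receipt of study drug. SAP section 3, on planned analyses, lists only the intent-to-treat and per-protocol sets as fixed before unblinding; if m-ITT were separate, that list would omit the primary set. Loose terminology for a single set is a fair reading. The SAP does not say so, however, and section 7 describes ITT and m-ITT in different terms. A rule that ends a trial should not depend on the reader's choice between them.

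**The gap is narrow.** This largely stands. Because the SAP's ITT requires receipt of drug, patients without surgery are outside both sets. If the interim analyses only those who completed follow-up, patients lost to aphasia or coma are outside both as well, which leaves mainly ineligibility found later. But the 424 is worded as a trigger for the look and not as a definition of who is analysed.

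**Any boundary can be crossed by one patient.** True. The point is that here one exclusion can separate two analyses of the same trial, and the plan does not rank them.

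**Stronger readings.** A reader might infer that the boundary no longer controls type I error. The calculation does not support that: the two statistics are very highly correlated and the overall error hardly moves. A reader might also suppose that harm needs large and unequal exclusions. Nothing in the documents points to such an imbalance among blinded staff and patients, and the simulation shows disagreement with equal exclusions. Finally, the mismatch alone is no argument for replacing m-ITT as the primary population; that is a separate question.

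**Conclusion.** The concern holds as a gap in the specification of a stopping rule. As written, the test that can end the trial and the primary test use different sets, and neither document says which governs after a stop. The consequence is a possible stop that the primary analysis does not confirm at 0.019: about 1% to 8% of stops under the planned effect if 1% to 5% of patients are excluded equally from both arms, and up to 12.5% at 10%. In nearly all such cases at 1% to 5% exclusions, the m-ITT p-value lies between 0.019 and 0.05.

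The size rests on assumed exclusion rates, equal exclusions, 212 patients per arm at the look and the planned remission rates. The finding on type I error also rests on an assumed final level of about 0.044. Neither the 0.019 figure nor the sample size is wrong on this account. The change is worth making because it is cheap and affects a decision that cannot be reversed, but the weight is modest.

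**What to change.** Add to SAP section 6:

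- The interim test uses the same analysis set as the primary test in SAP section 9, with membership fixed blind before the look.
- It uses the same missing-data rule as that primary test.
- If the trial stops early, this analysis is the primary result.
- The other set is reported as supportive at both looks.

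Amend the protocol's interim section to match. With one set at both looks, disagreement caused by the set disappears by construction. The 0.019 boundary and the planned 506 and 564 patients do not change. The only cost beyond a few sentences is the work of settling set membership blind before the interim as well as before the final analysis.
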